### **Power Considerations**

This is a pilot study and we plan to recruit 40 subjects for each study group. Our power calculation is mainly based on the binary primary outcome. We assume no more than 15% attrition rate, and assume no period

effect. In the following table, we give the power for detecting the superiority of Insulclock based on Exact Test for Binomial proportion with alpha=0.05, under different projections for the proportion of subjects showing treatment preference (i.e. adherent under one treatment but not under the other), denoted by Ptp, and projections for the probability of preference to Insulclock given showing treatment preference, denoted by p.

	P tp					
Power		90%	80%	70%	60%	50%
р	0.6	31.2%	28.2%	21.5%	17.8%	13.9%
	0.7	87.9%	83.7%	74.9%	66.5%	55.4%
	0.8	>99%	>99%	>99%	97.6%	93.8%
	0.9	>99%	>99%	>99%	>99%	>99%

Regarding the secondary outcomes, the power calculations can be made conservatively based on superiority hypotheses without specifying the equivalent margins. For continuous secondary outcomes, we would have over 80% power to detect outcome difference of 0.41 times the standard deviation based on paired t tests, with alpha=0.05, assuming equal outcome standard deviations for Insulclock and the conventional device, and within subject correlation equal to 0.3.

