### **Selection of Patients**

**Number of subjects planned.** The total number of patients with T2D to be included in this pilot study is 150. We anticipate a dropout rate of 10% - 20% through week 24 so that each arm will have 32 subjects at week 32.

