### Analysis of Primary Endpoint:

The primary outcome of treatment adherence with the use of Insulclock with feedback or no information (blinded) is whether a patient has a good adherent to the treatment regimen (assessed based on insulin omission, mistiming, and dosing). Given the 2 by 2 cross-over design, the superiority of the Insulclock system over the conventional insulin pen device will be determined by comparing the percent of patients showing a good treatment adherence with Insulclock but a poor treatment adherence with the conventional device to the percent of patients showing a poor treatment adherence with Insulclock but a good treatment adherence with the conventional device. We will perform this comparison based on McNemar's test assuming the period effect is negligible. We will further conduct logistic regression to accommodate potential period effect and adjust for other potential confounders. We will apply standard model selection and model checking procedures (such as the Hosmer-Lemeshow tests) to decide and evaluate the final model. A p value of <0.05 will be considered significant.

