# **STUDY SCHEDULE:**

FIRST PATIENT IN	2017 NOVEMBER
SCREENING	~200
RANDOMIZED	80
LAST PATIENT RECRUITED	2018
LAST PATIENT IN (COMPLETED)	2018 DECEMBER
DATA ANALYSIS	JUNE 2019- FEBRUARY 2019
SUBMISSION TO CONGRESS OR JOURNAL	ADA 2020 MAJOR MEDICINE JOURNAL AND/OR DIABETES CARE

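### The planned sample size (150 or 80) and the attrition behind the power table (15% or up to 20%) contradict each other and need to be reconciled

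*Combined protocol and SAP*

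**What the plan says.** The number of patients appears in three places.

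- Selection of Patients: "The total number of patients with T2D to be included in this pilot study is 150". It then allows 10% to 20% dropout through week 24, "so that each arm will have 32 subjects at week 32".
- Power Considerations: "we plan to recruit 40 subjects for each study group", so 80 in total, with attrition of no more than 15%.
- Study Schedule: about 200 screened and "RANDOMIZED 80".

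Duration of study gives a 26-week treatment phase and a safety follow-up at week 28.

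The primary power table is calculated "based on Exact Test for Binomial proportion with alpha=0.05". Its columns vary one input, the share of discordant patients, and the plan describes them as power "under different projections for the proportion of subjects showing treatment preference (i.e. adherent under one treatment but not under the other"). That proportion, P_tp, runs from 50% to 90%. The second axis is p, the probability that a patient who is adherent under only one condition is adherent under Insulclock; it runs from 0.6 to 0.9. For continuous secondary outcomes the same section claims over 80% power for a difference of 0.41 standard deviations, with "within subject correlation equal to 0.3".

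**The concern.** A reader cannot tell how many patients the trial will randomise or how many it expects to analyse. The power table is the only stated support for the primary comparison and depends directly on the completer count. If 150 is the real target, the table describes a much smaller trial. If 80 is the target, Selection of Patients is wrong, and its own 20% dropout gives fewer completers than the table assumes. Anyone judging recruitment, or later asking whether the trial reached its planned size, would get a different answer depending on the section read.

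**Working it through.** **Completers under each statement** (taking arm to mean randomised sequence group)

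- Power Considerations: 2 × 40 = 80; 80 × 0.85 = 68.
- Selection of Patients, worst case applied to 80: 80 × 0.80 = 64 = 2 × 32. This matches the stated 32 per arm.
- Selection of Patients, applied to its own 150: 150 × 0.80 / 2 = 60 and 150 × 0.90 / 2 = 67.5 per arm. Reaching 32 per arm from 150 would need a loss of 1 − 64/150 = 57%.
- Time point: week 32 is 6 weeks after the 26-week treatment phase and 4 weeks after the week-28 follow-up. The same sentence counts dropout only to week 24.

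**Reproducing the printed table.** Fix the number of discordant patients at 68 × P_tp, rounded: 61, 54, 48, 41, 34. Test p = 0.5 with an exact binomial test, rejecting when the upper tail is at most 0.025. The sidedness is not stated, but only the two-sided version fits. The p=0.7 row comes out as 87.9/83.7/74.9/66.5/55.4%, exactly as printed, and all 20 cells agree to within 0.1 point. The table therefore rests on 68 completers.

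**Effect of 64 completers.** Holding the discordant count fixed makes exact power jump with rounding, so a comparison of two sample sizes is better averaged over that count:

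averaged power = Σ over n of Binomial(n; N, P_tp) × power(n, p).

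| Completers N | p | P_tp 90% | 80% | 70% | 60% | 50% |
|---|---|---|---|---|---|---|
| 68 | 0.7 | 87.0 | 82.7 | 76.9 | 69.2 | 59.1 |
| 64 | 0.7 | 85.0 | 80.2 | 74.0 | 65.9 | 55.8 |
| 68 | 0.8 | 99.9 | 99.7 | 99.1 | 97.7 | 94.2 |
| 64 | 0.8 | 99.8 | 99.5 | 98.7 | 96.8 | 92.6 |

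On the plan's fixed-count basis, 64 completers give 58, 51, 45, 38 and 32 discordant patients. The p=0.7 row is then 87.9/83.6/74.6/65.9/49.5%, almost unchanged except at P_tp 50% (49.5% against the printed 55.4%).

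**Effect of 150 patients.** With 150 × 0.80 = 120 completers, the averaged formula at p=0.7 gives 98.7/97.6/95.5/92.1/86.2%. At P_tp 50% that is 86% against 56% with 64.

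**Continuous secondary outcomes.** The SD of a within-patient difference is √(2 × (1 − 0.3)) = 1.183 SD, so the standardised effect is 0.41 / 1.183 = 0.347. The noncentrality is 0.347 × √68 = 2.86 with 68 completers and 0.347 × √64 = 2.77 with 64. The noncentral t distribution (two-sided 0.05) gives 80.4% and 77.9%. The claim of over 80% holds at 68 completers but not at 64.

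**The case against.** The best defence is that 80 is clearly the intended number. It appears in two sections, and the 32 per arm in the third also fits it, so 150 and week 32 may be leftovers. Alternatively, 150 might count patients entering the device-training week, some of whom become screen failures before randomisation. Either is possible, but the documents say neither: the Study Schedule goes from about 200 screened to 80 randomised without a 150, and Selection of Patients takes its dropout and per-arm figures directly from its 150. It is also fair that this is a pilot, that no table cell is named as the design target, and that moving from 68 to 64 completers costs only about 2 to 3 points at p=0.7. Those points limit the size of the problem but do not remove the contradiction.

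A reader might go further and infer that the table itself is unsound. If P_tp and p are both given, the largest possible within-patient correlation occurs when concordant patients split evenly:

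[((1 − P_tp)/2)² − p(1 − p)P_tp²] / [((1 − P_tp)/2 + p·P_tp) × ((1 − P_tp)/2 + (1 − p)·P_tp)].

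For p=0.7 and P_tp 80% this is (0.01 − 0.1344) / (0.66 × 0.34) = −0.55; at 90% it is −0.77. Fifteen of the 20 cells require negative correlation, including the printed 87.9% and 83.7%. That looks unlikely for the same patients observed twice, though this is a judgement: the plan's +0.3 is stated for continuous outcomes only. It does not follow that the table is wrong or the trial underpowered. Every cell is a possible distribution. The assumed difference in adherence is P_tp × (2p − 1), so the 83.7% cell assumes 0.8 × 0.4 = 32 points. The same 32 points at zero correlation gives 95% to 97% exact power with 68 completers (assuming comparator adherence of 30% to 50%). The plan also prints less favourable p=0.7 cells, down to 55.4%.

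Nor is there a conflict between the exact binomial power calculation and the analysis section's "We will perform this comparison based on McNemar's test". The exact binomial test on discordant patients is the exact form of McNemar's test.

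**Conclusion.** The contradiction holds as written. The plan gives two sample sizes, 150 and 80. Its 32 per arm is compatible only with 80, at the 20% end of its dropout range, and is attached to a week the study does not reach. Its power table assumes 68 completers where another section allows 64.

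If 80 is intended, the consequence is small: at p=0.7 averaged exact power falls from 59–87% to 56–85% across the printed P_tp range, p=0.8 stays above 92%, and the secondary-outcome figure drops from just above 80% to about 78%. If 150 is intended, the table considerably understates power. These figures assume a two-sided exact test, no period effect (as the plan does) and every completer evaluable in both periods. They do not show that the printed table is miscalculated or that the trial is too small.

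**What to change.** 1. State one number to be randomised, the same in Selection of Patients, Power Considerations and the Study Schedule. If 150 counts something other than randomised patients, say what.
2. State one attrition range and one time point for the expected completers, within the study's stated duration.
3. Recompute the primary power table and the secondary-outcome statement for the lowest completer count the plan expects. Say that the test is two-sided and whether the discordant count is fixed or averaged. If the count is 64, the rows under working can be used.

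Optional, as an aid to interpretation only: add P_tp columns of 20% to 40% and show the implied adherence difference, P_tp × (2p − 1), beside each cell.

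The cost is a few corrected sentences and one recomputed table. If 80 is confirmed, the stated power becomes slightly less favourable and no extra patients are needed. If 150 is confirmed, the recruitment figures in the Study Schedule must change as well.

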# Data Handing and Record Keeping:

Data collection records with personal identifiers will be stored in locked file cabinets. Presentation of the study results at regional or scientific meetings or in publications will not identify subjects. Access to research and confidential records will be limited to clinical investigators, research coordinators, and the IRB at Emory University.

# Ethics:

# **Informed Consent.**

After identification of eligible patients these individuals will be provided basic information regarding the study and, if interested, a member of the research staff using inclusion/exclusion criteria delineated elsewhere in the protocol will enroll patients. Informed consent will be obtained before any trial related procedures including screening procedures. The consent form, potential risks and benefits, and the rights of research participants will be explained to the participant by the investigators or research coordinator. Individuals will be asked if they have questions, and a member of the research staff will answer questions. The principal investigator will also be available always to answer questions that participants may have during the consent procedure or during the time a participant is enrolled in the study. The consent form will be provided in accordance with the IRB guidelines of Emory University. A signed copy of the consent form will be provided to the participant and a copy will be placed in the file that is maintained for each participant in the study office.

Informed consent will follow the procedure of Emory University Institutional Review Board. Every potential participant will be informed in writing and verbally with the important and key points of the study. One of the investigators or research coordinators will obtain a witnessed informed consent prior to inclusion of a patient into the study.

The study will be conducted in accordance with the Declaration of Helsinki and will be conducted in accordance with the ICH GCP guidelines. The sponsor-investigator will comply with all applicable regulatory and legal requirements, ICH GCP guidelines and the Declaration of Helsinki in obtaining and documenting the informed consent.

# **STUDY SCHEDULE:**

FIRST PATIENT IN	2017 NOVEMBER
SCREENING	~200
RANDOMIZED	80
LAST PATIENT RECRUITED	2018
LAST PATIENT IN (COMPLETED)	2018 DECEMBER
DATA ANALYSIS	JUNE 2019- FEBRUARY 2019
SUBMISSION TO CONGRESS OR JOURNAL	ADA 2020 MAJOR MEDICINE JOURNAL AND/OR DIABETES CARE

# **Payment for Participation:**

Participation in this study is voluntary. Patients will receive seventy- five dollars (\$75, 00) after each clinic visit. Total compensation will be four hundred and fifty dollars (\$450).

